3.3 HYPOTHESIS

The overarching hypothesis is that administration of corticosteroids to pregnant women with either pre-gestational or gestational diabetes within 7 days prior to planned CS where CS is scheduled between 35⁺⁰ weeks and 39⁺⁶ gestation will reduce the incidence and severity of neonatal respiratory morbidity without adverse short-term (within the first 6 weeks) consequences for the mother or baby.

Specifically, we hypothesise that administration of corticosteroids to women with pre-gestational or gestational diabetes within 7 days prior to planned CS, where CS is scheduled between 35⁺⁰ weeks and 39⁺⁶ gestation, will:

1. reduce the incidence and severity of neonatal respiratory morbidity.
2. not increase the incidence of neonatal hypoglycaemia.
3. not increase the incidence of maternal morbidity (hyperglycaemia, chorioamnionitis, endometritis, or wound infection).
4. increase breast feeding rates at hospital discharge and 6 weeks post-partum.
5. reduce health care costs.

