- maternal general health prior to randomisation and at 6 weeks post partum assessed using the SF12⁵⁸ and AQoL8D.⁵⁹
- breast feeding rates at hospital discharge and 6 weeks' post-partum.

[figure not shown]
Assessment of blinding: We will assess the ability to blind participants, clinicians and research staff to the treatment allocation in a subset of participants. This information will be used in interim analyses (if required) and will be collected and reported to ensure transparency regarding the conduct of the trial.

Health economics: We will assess the economic costs and benefits of this intervention at 6 weeks post partum and again at 2 years post partum under the supervision of [name], who is a health economist. This will involve estimating the costs of administering the intervention compared with not administering the intervention. The hospital costs associated with each infant's birth admission will be obtained from administrative records and will reflect factors such as length of stay and admission to the neonatal nursery. Incremental cost effectiveness will be presented as a cost per case of respiratory morbidity avoided, a cost per case of respiratory support avoided and a cost per neonatal nursery admission avoided for the intervention group compared with the placebo group. Extensive one way and probabilistic sensitivity analyses will be conducted.

STUDY DESIGN

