All participants will be instructed to monitor their blood glucose using a capillary blood glucose monitor prior to every meal and 2 hours following meals for 72 hours after the first injection. Participants will be asked to record all blood glucose readings via REDcap with the link provided at the time of randomisation. Women who normally use continuous glucose monitoring or flash glucose monitoring should be advised to use capillary blood glucose monitoring according to the above schedule during this time period in addition to their continuous or flash blood glucose monitor. All participants will be provided with a site specific information sheet which will provide information about target blood sugars and what to do in the event of hypoglycaemia or hyperglycaemia. Women who experience hyperglycaemia will be advised to contact

the relevant staff at the participating site for advice regarding insulin titration. Maternal hyperglycaemia will be managed in accordance with local protocols with the aim being to ensure euglycaemia as much as possible. Staff who provide advice regarding the management of hyperglycaemia will be encouraged not to disclose whether they suspect the participant receive bethamethasone or placebo. Guidance regarding insulin management is provided in the PRECeDe Insulin Management Guideline (see Appendix 2) however relevant staff at each site will be responsible for individualising the care.

While, there is no requirement for women who are otherwise well to be admitted during the period between randomisation and the CS, individual sites may choose to arrange routine admission for close surveillance if that is their usual practice. Admission for close surveillance is recommended in the event of significant maternal hyperglycaemia or hypoglycaemia.

Monitoring of neonatal blood glucose and treatment of neonatal hypoglycaemia

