After discharge of the mother and baby from hospital after the birth, the health outcome data will be collected from the case records by the research midwife at the recruiting centre and entered into a purpose built REDCap database.

Women and their children will be followed up after discharge from hospital with questionnaires regarding additional maternal morbidity (wound infections, mental health) and neonatal morbidity (respiratory illness, method of feeding, and feeding difficulties) completed at 6 weeks' postpartum. In addition we will collect health information via the standardised SF12, EPDS and the AQoL-8D. Women who score ≥ 13 on the EPDS will be contacted by the lead investigator / trial coordinator at the respective site to assess maternal well being and will be directed to appropriate resources according to local guidelines.

All data will be entered into a REDCap database stored on a secure password protected server at The University of Melbourne.

Childhood Follow-Up: We will seek permission for on-going contact at least annually with mothers and their infants as part of the consent process. This contact will take the form of an email message with an annual 'birthday card' sent to the email address as well as an SMS request to update participant contact details. Future childhood follow-up studies are planned and separate funding will be sought to undertake these studies. All future studies will require HREC approval.

Emergency Unblinding: Unblinding is unlikely to be required for management of a participant with an adverse event as the effect of antenatal corticosteroids is generally short lived. However, emergency unblinding will be possible and can be arranged by contacting the Trial Coordinator or Coordinating Principal Investigator.

STUDY TABLE

Procedures	Assessment / Procedure	Screening (after 32 weeks)	Randomisation (within 7 days of planned elective CS)	First dose of betamethasone or placebo	Second Dose of Betamethasone or placebo (24 hours after first dose)	Caesarean Section and Post birth visit / data collection	Discharge of mother and baby	6 week follow-up	Annual follow-up
	Informed Consent	X							
	Demographic Information Weight & Height Measurement		X						
	Administration of Betamethasone or placebo			X	X				
	Symptoms questionnaire					X		X	
	Completion of EPDS, SF12, AQuOL 8D		X					X	
	Collection of data about blood glucose measurements and insulin doses			X	X	X			
	Collection of birth and neonatal data					X	X		

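### The 2-year economic assessment has no data source in this protocol, and the cost items it names leave out maternal care and readmissions that the trial itself anticipates and records

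*Protocol*

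**What the plan says.** Cost-effectiveness is a secondary objective (Synopsis) and a secondary aim (Section 3.4). The fifth specific hypothesis in Section 3.3 is that treatment will "reduce health care costs".

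The health economics paragraph of Section 4 sets the time points: "We will assess the economic costs and benefits of this intervention at 6 weeks post partum and again at 2 years post partum". It then describes the costs in two sentences. The first is "This will involve estimating the costs of administering the intervention compared with not administering the intervention". The second gives a source: "The hospital costs associated with each infant's birth admission will be obtained from administrative records", with length of stay and nursery admission as the drivers. Results are to be shown as three ratios. The first is introduced by "Incremental cost effectiveness will be presented as a cost per case of respiratory morbidity avoided"; the other two use respiratory support and nursery admission as the event averted. One-way and probabilistic sensitivity analyses are promised.

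On follow-up beyond 6 weeks, Section 5.1 says: "Future childhood follow-up studies are planned and separate funding will be sought to undertake these studies". On maternal care between injection and birth, the same section says: "Admission for close surveillance is recommended in the event of significant maternal hyperglycaemia or hypoglycaemia".

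**The concern.** There are two separate problems.

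The first is a contradiction. A 2-year economic result needs resource use or outcomes measured up to 2 years, and the schedule contains none. An analysis plan cannot repair this, because it can only analyse what the protocol collects.

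The second is the scope of the costs. The Synopsis associates betamethasone with maternal hyperglycaemia, and Section 5.1 links significant hyperglycaemia to admission. The care most likely to be added by the drug therefore falls largely on the mother, yet both named cost items lie elsewhere. If only those items were costed and maternal care did rise, the trial could report support for its cost hypothesis although the total cost for mother and baby had fallen by less, or not at all.

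**Working it through.** **Time horizon.** Set side by side:

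- Section 4: economic assessment at 6 weeks and at 2 years.
- Section 5.1, study table: the last health, feeding, wound and questionnaire data are at 6 weeks. The only later column is annual, and its only entry is the e-mail card and text message about contact details.
- Section 5.1, Childhood Follow-Up: later studies need separate funding and their own ethics approval. Section 3.4 likewise leaves them to future applications.
- Section 4, cost source: administrative records are named for the birth admission only. No record linkage or resource questionnaire to 2 years is described.

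So there is a stated 2-year output and no stated 2-year input.

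**Cost scope.** Each item of care against where it appears:

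| Item | Anticipated or recorded in | Named as a cost in Section 4 |
|---|---|---|
| Giving the intervention | Section 5.1 | Yes |
| Infant birth admission, including nursery stay | Section 4 | Yes |
| Mother's admission before caesarean section | Recommended in some cases in Section 5.1; secondary outcome in Section 4; SAE if unplanned (Section 12.1) | No |
| Extra insulin for the mother | Secondary outcome in Section 4; Appendix 2; concomitant medication in Section 5.1 | No |
| Mother's birth admission | Section 5.1, discharge data collection | No |
| Readmission of mother or baby | SAE in Section 12.1 | No |

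**Consequence for the ratios.** The plan states no economic figure, so there is none to reproduce. The denominator can be taken from Section 8.1, where respiratory distress falls from 6% to 3%, a difference of 0.03. That design does reproduce. The usual two-proportion formula at two-sided 0.05 and 90% power gives 1002 per arm, or 1068 with continuity correction. Then 1068 / 0.97 = 1101.03, rounded up to 1102 per arm, or 2204 in total against the stated 2200.

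Let A be the extra cost of giving the intervention, I the difference in infant birth-admission cost, and M the difference in all unnamed costs. Each is a mean per woman, betamethasone minus placebo. Let d be the absolute reduction in respiratory morbidity, with one infant per woman for simplicity.

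- Ratio on the named items: (A + I) / d
- Ratio on all items: (A + I + M) / d
- Difference: M / d

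Per currency unit of M:

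- d = 0.03: 1 / 0.03 = 33.3
- d = 0.015: 1 / 0.015 = 66.7
- d = 0.01: 1 / 0.01 = 100

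Only d = 0.03 comes from the protocol; the smaller values are assumed, to show the range. M itself cannot be computed: the protocol gives no unit cost, no maternal admission rate and no insulin quantity. If M is above zero, the named-items ratio is too favourable to betamethasone; if M is zero, nothing is lost.

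**The case against.** The strongest reply is that maternal costs are unmentioned, not excluded. The paragraph describes what the evaluation will involve and does not present a closed list. A full cost list could reasonably sit in an analysis plan that is not shown, and most of the events needed are already recorded. This stands. A reader might infer that the protocol rules maternal costs out, and the text does not say so. What remains is that it names a cost source for the infant and none for the mother, although its hypothesis concerns health care costs generally.

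A reader might also infer that the whole evaluation leans towards savings. The documents do not support that:

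- The missing 2-year data have no known direction of bias.
- The infant cost item covers the whole birth stay, so nursery care for neonatal hypoglycaemia, a main feared harm, is counted.
- The three ratios do not all use outcomes expected to improve. Nursery admission is listed in the Synopsis among outcomes examined for an increase. In the protocol's own non-randomised data (Table 1) it was 54% with steroids and 44% without, odds ratio 1.49 (95% CI 0.86 to 2.57).
- The third specific hypothesis in Section 3.3 is that maternal morbidity, including hyperglycaemia, will not rise, so the sign of M is open.

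Nor would a rise in maternal admissions go unseen, because admission before caesarean section is a secondary outcome. It would be absent only from the cost figure, and only if the named items were the full list. A break-even rise in maternal admissions could be produced by assuming a ratio of nursery to maternal admission cost, but nothing in the documents supports any such ratio.

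On the time horizon, the Synopsis does list 2 years as a point for the future cohort, so the 2-year evaluation may be meant to belong there. That makes the repair easy, but Section 4 as written presents it as an output of this trial.

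**Conclusion.** Both parts hold, within limits. The 2-year economic result cannot be delivered from the data this protocol collects; this rests on the text alone and needs no assumption. The named costs omit maternal care and readmissions that the trial anticipates and records. Costing only those items would favour betamethasone on two conditions: that the named items are the whole costing, and that the unnamed care increases with treatment. The size of that effect is not computable from the documents. The factor of 33.3 per currency unit shows only how an uncounted cost per woman scales into the cost per case, and it depends on the planned 3-point reduction being achieved. The primary outcome and the safety analyses are unaffected.

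**What to change.** In Section 4:

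1. State that costs cover mother and infant(s) from randomisation to 6 weeks: maternal antenatal admission, the birth admissions of both, additional insulin, and readmission of either, as well as the cost of giving the intervention.
2. Report the incremental cost per mother with her infant(s) alongside the three ratios, since that difference is what the cost hypothesis concerns.
3. Limit this protocol's economic evaluation to 6 weeks and assign the 2-year evaluation to the separately funded follow-up.

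This is mainly a change of wording. Admissions before caesarean section, insulin use and readmissions are already captured as outcomes, concomitant medications or SAEs, so the added work is attaching costs to them, for example by querying administrative records for the mother as well as the infant. The price is a little more costing work and a cost result that may look less favourable.

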5.1 STUDY TYPE & DESIGN & SCHEDULE

The PRECeDe Randomised Trial is an international multicentre, randomised, triple blind, placebo controlled trial (Figure 4).

Trial setting: The trial will be conducted in maternity units throughout Australia and New Zealand

Trial entry: Women will be identified and counselled by trained research midwives. Written consent will be obtained. In accordance with the CONSORT statement⁶⁰ we will collect data regarding the number of eligible participants, the number approached, and the number of participants who decline to take part in the trial via a waiver of consent to collect deidentified data regarding potentially eligible participants.

Randomisation: Eligible, consenting women will be randomised using a computer generated random number sequence. The randomisation schedule, using a 1:1 randomisation and variable block size will be prepared in advance.

Randomisation will be stratified by:

- Type of diabetes (Type 1 diabetes, Type 2 Diabetes, Gestational Diabetes)
- Gestation at delivery (35⁺⁰ to 36⁺⁶ and 37⁺⁰ to 38⁺⁶ weeks, 39⁺⁰ to 39⁺⁶ weeks)
- Recruiting site

Randomisation can only take place within 7 days prior to planned elective CS and at least 24 hours prior to planned elective CS to allow two doses of betamethasone to be administered prior to birth. Randomisation can occur within the week prior to 35⁺⁰ weeks gestation as long as the planned CS is scheduled after 35⁺⁰ weeks gestation.

Treatment Allocation: Assignment is to either the 'betamethasone group' or the 'placebo group'. A study number will be allocated to the participant that corresponds to the relevant trial treatment pack, each of which look identical and contain two masked syringes each containing either 11.4 mg of Celestone Chrondose in 2 ml (betamethasone 11.4 mg, as betamethasone sodium phosphate and betamethasone acetate) or placebo (normal saline 2 ml), both of which will be supplied and packaged by Baxter Healthcare Corporation who have confirmed stability testing for both the active drug and placebo for 180 days. Syringes will be masked with red tape to ensure that the volume of contents can be assessed but the betamethasone suspension will not be distinguished from the clear solution of the placebo. The syringes will be packaged with the appropriate randomisation number by Zeullig Pharma. All drugs will be prescribed by a medical practitioner as "Betamethasone 11.4mg in 2 ml, x2 doses or Normal Saline Placebo 2 ml, x 2 doses" and dispensed by Pharmacy staff at the recruiting site according to the allocated randomisation number.

Treatment schedules: Women in both treatment groups will be given the contents of one of their allocated syringes intramuscularly at least 24 hours prior to the planned CS. The second injection will be retained at the site and administered 24 hours (\pm 4 hours) later. Researchers, participants and staff will be blinded to the treatment allocation. If birth is required less than 24 hours after the first injection (for example, if the CS time must be brought forward due to maternal or fetal issues (eg spontaneous onset of labour), the second injection will be withheld. The reasons for not administering the second injection will be recorded on the CRF. The second injection should not be given earlier than 20 hours after the first injection. Failure to administer the second injection does not constitute withdrawal from the trial. There is no minimum amount of time required between the second injection and the CS.

If the CS is delayed beyond 7 days following administration of the two injections, repeat study medication (or antenatal corticosteroids) should not be administered.

Standard Care: Care for both groups will otherwise be according to standard practice for women with diabetes and their infants.

Monitoring of maternal blood sugars and treatment of maternal hyperglycaemia

All participants will be instructed to monitor their blood glucose using a capillary blood glucose monitor prior to every meal and 2 hours following meals for 72 hours after the first injection. Participants will be asked to record all blood glucose readings via REDcap with the link provided at the time of randomisation. Women who normally use continuous glucose monitoring or flash glucose monitoring should be advised to use capillary blood glucose monitoring according to the above schedule during this time period in addition to their continuous or flash blood glucose monitor. All participants will be provided with a site specific information sheet which will provide information about target blood sugars and what to do in the event of hypoglycaemia or hyperglycaemia. Women who experience hyperglycaemia will be advised to contact

the relevant staff at the participating site for advice regarding insulin titration. Maternal hyperglycaemia will be managed in accordance with local protocols with the aim being to ensure euglycaemia as much as possible. Staff who provide advice regarding the management of hyperglycaemia will be encouraged not to disclose whether they suspect the participant receive bethamethasone or placebo. Guidance regarding insulin management is provided in the PRECeDe Insulin Management Guideline (see Appendix 2) however relevant staff at each site will be responsible for individualising the care.

While, there is no requirement for women who are otherwise well to be admitted during the period between randomisation and the CS, individual sites may choose to arrange routine admission for close surveillance if that is their usual practice. Admission for close surveillance is recommended in the event of significant maternal hyperglycaemia or hypoglycaemia.

Monitoring of neonatal blood glucose and treatment of neonatal hypoglycaemia

Neonatal care for all infants will be in accordance with local protocols for the management of infants born to women with diabetes. At a minimum, all infants will undergo blood glucose testing (preferably using a glucose oxidase method (eg i-STAT or blood gas analyser) within the first 2 hours of life and then every 3-4 hours until 3 consecutive blood glucose recordings $>2.6\text{mmol/L}$. Further management including the treatment of hypoglycaemia and the timing of subsequent blood glucose measurements will be determined according to the local site algorithms. Where a site does not have a local algorithm, we recommend that Australian sites follow the Safer Care Victoria algorithm (Appendix 3) and New Zealand sites follow the Auckland DHB algorithm (Appendix 4)

Concomitant Medications / Treatments: All concomitant medications received by both the mother following randomisation, and the infant following birth, up until the time of discharge home following birth will be recorded. There are no restrictions regarding concomitant medications except antenatal corticosteroids (which constitute an exclusion criterion if received at any time before randomisation).

Compliance: Compliance with the allocated treatment schedule will be recorded, however as analysis will be by intention to treat, non-compliance with the allocated treatment schedule (including failure to complete the two injections) will not be regarded as an indication for exclusion or withdrawal from the trial.

Assessment of Blinding: The ability to retain blinding will be assessed in a subset of the participants if required (see section 7.4 Trial Risks). The following participant staff groups will be asked to predict which group the participant was allocated to (Betamethasone or Placebo or uncertain).

and their reason for this

- Participants
- Any staff members providing care for the participant or her baby
- Research staff involved in collection of outcome data

Data Collection: Prior to discharge following birth, participants will be asked by the site research team to complete a questionnaire about any side effects following trial medication administration. This will include questions regarding a range of symptoms including pain at the site of injection, flushing, fatigue, nausea, headaches, visual changes, changes in fetal movement patterns, hyperglycaemia, hypoglycaemia and adjustments to insulin doses.

After discharge of the mother and baby from hospital after the birth, the health outcome data will be collected from the case records by the research midwife at the recruiting centre and entered into a purpose built REDCap database.

Women and their children will be followed up after discharge from hospital with questionnaires regarding additional maternal morbidity (wound infections, mental health) and neonatal morbidity (respiratory illness, method of feeding, and feeding difficulties) completed at 6 weeks' postpartum. In addition we will collect health information via the standardised SF12, EPDS and the AQoL-8D. Women who score ≥ 13 on the EPDS will be contacted by the lead investigator / trial coordinator at the respective site to assess maternal well being and will be directed to appropriate resources according to local guidelines.

All data will be entered into a REDCap database stored on a secure password protected server at The University of Melbourne.

Childhood Follow-Up: We will seek permission for on-going contact at least annually with mothers and their infants as part of the consent process. This contact will take the form of an email message with an annual 'birthday card' sent to the email address as well as an SMS request to update participant contact details. Future childhood follow-up studies are planned and separate funding will be sought to undertake these studies. All future studies will require HREC approval.

Emergency Unblinding: Unblinding is unlikely to be required for management of a participant with an adverse event as the effect of antenatal corticosteroids is generally short lived. However, emergency unblinding will be possible and can be arranged by contacting the Trial Coordinator or Coordinating Principal Investigator.

STUDY TABLE

Procedures	Assessment / Procedure	Screening (after 32 weeks)	Randomisation (within 7 days of planned elective CS)	First dose of betamethasone or placebo	Second Dose of Betamethasone or placebo (24 hours after first dose)	Caesarean Section and Post birth visit / data collection	Discharge of mother and baby	6 week follow-up	Annual follow-up
	Informed Consent	X							
	Demographic Information Weight & Height Measurement		X						
	Administration of Betamethasone or placebo			X	X				
	Symptoms questionnaire					X		X	
	Completion of EPDS, SF12, AQuOL 8D		X					X	
	Collection of data about blood glucose measurements and insulin doses			X	X	X			
	Collection of birth and neonatal data					X	X		
	Collection of participant assessment of blinding (subset of participants)						X		
	Collection of staff assessment of blinding (subset of participants)						X		
	Collection of maternal and neonatal outcome data (including neonatal blood glucose)						X		
	Collection of Mothers and babies health, breastfeeding and wound infection data							X	
	Completion of postpartum questionnaires							X	

	Annual email birthday card and SMS request to confirm contact details									X
--	---	--	--	--	--	--	--	--	--	---

